## 5.5 Safety Analysis

Safety will be assessed by evaluation of the following variables:

- Adverse events
- Safety laboratory (haematology, biochemistry, urinalysis)
- Vital signs (blood pressure, heart rate)
- 12-lead electrocardiogram (ECG)
- Columbia-Suicide Severity Rating Scale (C-SSRS)
- Movement Disorder Society-sponsored version of Unified Parkinson's Disease Rating Scale (MDS-UPDRS)
- Questionnaire for Impulsive-Compulsive Disorders in Parkinson's Disease – Rating Scale (QUIP RS)

The safety set will be used for the analysis of the safety data.

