Continuous efficacy endpoints – the change from baseline at each key visit (end of treatment period I, II, and III) in ESS, PVT and MoCA - will be analysed using a mixed linear regression model. The model will include the treatment, period, treatment by period interaction, sequence, and baseline scores as fixed effects, and the subject nested within sequence as a random effect.

Categorical efficacy endpoints – absence of residual somnolence and ESS responder status at each key visit – will be analysed using a mixed effects logistic regression model, with the treatment, period, treatment by period interaction, sequence, and baseline scores as fixed effects, and the subject nested within sequence as a random effect.

Treatment least square means and mean differences will be reported with their standard errors and 95% confidence intervals. The significance of the differences between Treatment A (THN102 Placebo), Treatment B (THN102 200/2) and Treatment C (THN102 200/18) will be assessed with a contrast t-test at the two-sided 5% level.

Supportive analysis

The same analysis will be repeated on the PP set, to assess robustness of the analysis of the variables from ESS and PVT and possibly on other efficacy results. Subgroup analyses may be performed to investigate the effect of the main demographics (age, gender) and disease characteristics (in terms of daily sleepiness extent, and cognitive impairment) on the efficacy outcomes.

The presence of a significant treatment by period interaction term in the main model may indicate a residual treatment (carryover) effect. In case of a significant treatment by period interaction, period I results will be analysed separately, and further analyses will be performed to explore the carry-over effects. The methods for evaluation of carryover effects will be defined in the SAP.

Safety analysis

Safety data will be summarised using summary statistics and frequency tabulations, as appropriate.

Pharmacokinetics

- Plasma concentrations of modafinil and flecainide at visits VR, V1B, V1C, V2B, V2C and V3B, considering time after last IMP intake.
- Concentration-time data per treatment and subject for modafinil and for flecainide. Plasma concentrations and time post IMP intake, to assess range of exposure at steady state for each treatment.

Trial flow chart

	VS1	VS2	VR	V1A	V1B	V1C	V2A	V2B	V2C	V3A	V3B/ EDV ¹¹	V3C

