1.3. Rationale for Trial Design and Dose Selection

1.3.1. Trial design

This proof-of-concept, phase IIa trial with THN102 should collect a sufficient body of information to assess the safety and efficacy profile of THN102 versus placebo in Parkinson's disease subjects suffering from excessive daytime sleepiness. The sample size required for a crossover design is approximately one third of the size required in a parallel trial. To use a cross-over option is thus a viable alternative design, with a sample size of about 60 subjects in this condition. In addition, a direct comparison between THN102 doses can be performed in the same subject. The selected trial design for this pilot proof-of-concept phase IIa trial is consequently a randomised, placebo-controlled, 3-way cross-over trial design comparing two dose levels of THN102 to placebo and followed by a washout period of 1-2 weeks. It was perceived as essential to take advantage of the cross-over design for exploring two doses of THN102 and comparing their impact on safety, ESS and other efficacy endpoints. The treatment duration of 2 weeks per period appears sufficient to observe therapeutic activity as the steady state will be reached after about 3 days of drug intake. Each treatment period is followed by a one-week washout period, which can be extended up to two weeks. In addition to the key efficacy endpoint, ESS, other efficacy endpoints have been selected, such as cognitive assessments including PVT and MoCA before and after each treatment period.

A difference of 25% in ESS is considered clinically relevant. [26] Therefore responder rates will be analysed, with responders being defined as subjects with at least 25% improvement from baseline.

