2. OBJECTIVES

2.1. Primary Objective

- To assess the safety profile of THN102 (modafinil/flecainide combination) at two doses (200 mg/18 mg and 200 mg/2 mg) versus placebo in subjects with excessive daytime sleepiness associated with Parkinson's disease (PD).

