8.3.2. Safety

Safety parameters will be analysed as follows:

Vital signs: All vital signs data will be listed by treatment, subject, and visit/time and will be flagged vs. predefined clinical normal range. The mean value of vital sign parameter assessments during a visit will be summarized. Summary statistics will be provided by treatment and visit/time. Shift tables will be provided for vital sign abnormality change from baseline to endpoint within each treatment period.

ECG parameters: All ECG parameters data will be listed by treatment, subject, and visit/time and abnormalities will be flagged vs. predefined clinical normal range. Summary statistics will be provided by treatment and visit/time.

A shift table will be prepared to document QT change and distribution vs. baseline.

C-SSRS: C-SSRS score data will be listed by treatment, subject, and visit/time. Summary statistics will be provided by treatment and visit/time.

QUIP-RS: QUIP-RS score data will be listed by treatment, subject and visit/time. Summary statistics will be provided by treatment and visit/time.

MDS-UPDRS: MDS-UPDRS score data will be listed by treatment, subject and visit/time. Summary statistics for each part of the MDS-UPDRS as well as the total score will be provided by treatment and visit/time.

Clinical laboratory evaluations: All laboratory data will be listed by treatment, subject, and visit/time and abnormalities will be flagged vs. common normal range if considered by investigator as clinically relevant. Summary statistics will be provided by treatment and visit/time. Shift tables will be provided for clinical laboratory variables' change from baseline to endpoint.

Adverse events: All information obtained on adverse events will be displayed by treatment and subject after coding with pertinent MedDRA version. All adverse events and related adverse events will be presented. The number and percentage of subjects with adverse events will be tabulated by body system and preferred term with a breakdown by treatment. An adverse event starting in one period and continuing into the next period is counted only in the onset period. A subject with multiple adverse events within a body system is only counted once towards the total of this body system.

Concomitant medications / Significant non-drug therapies: All concomitant therapies will be coded by WHO version and listed by treatment group and subject.

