## 2. OBJECTIVES AND DESIGN

### 2.1 Trial Objectives

#### 2.1.1 Primary Objective

The primary objective of this trial is to assess the safety profile of THN102 (modafinil/flecainide combination) at two doses (200 mg/18 mg and 200 mg/2 mg) versus placebo in subjects with excessive daytime sleepiness associated with Parkinson's disease (PD).

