- **TEAEs leading to death:** selected as those events where outcome of event is indicated as “fatal”.

The **duration of the AE** will be calculated using the following formula:

$$AE \text{ Duration (days)} = AE \text{ stop date} - AE \text{ start date} + 1$$

If the start or stop dates of the AE are incomplete or AE is still ongoing at the end of the trial, the duration will not be calculated.

The following tables and listings will be provided:

Table 15.2.1.1.1.S Overall Summary of TEAEs – Safety

Table 15.2.1.1.2.T Overall Summary of TEAEs – Safety

An overview of TEAEs:

- TEAE
- Non-Serious TEAE
- Serious TEAE
- Related TEAE
- Related Serious TEAE
- Severe TEAE
- TEAE leading to discontinuation
- Serious TEAE leading to discontinuation
- Related TEAE leading to discontinuation
- TEAE leading to death

will be displayed for the subjects in the safety set.

Table 15.2.1.2.T Incidence of TEAEs – Safety

Table 15.2.1.3.T Incidence of Non-Serious TEAEs – Safety

Table 15.2.1.4.T Incidence of Serious TEAEs – Safety

Table 15.2.1.5.T Incidence of Related TEAEs – Safety

Table 15.2.1.6.T Incidence of Related Serious TEAEs – Safety

Table 15.2.1.7.T Incidence of TEAEs Leading to Discontinuation – Safety

Table 15.2.1.8.T Incidence of TEAEs Leading to Death – Safety

TEAEs will be summarised by displaying the numbers of adverse events, as well as counts and percentages of subjects having experienced adverse events. Percentages will be based on the number of subjects in the safety set. SOC and PTs within each SOC will be ordered by descending overall incidence.

Table 15.2.1.9.T Incidence of TEAEs by Severity – Safety

TEAEs will be summarised similarly as above within each adverse event severity level.

All adverse event data will be listed as follows:

Listing 16.2.6.1 Adverse Events: MedDRA Coding

Listing 16.2.6.2 Adverse Events: General – Enrolled

Listing 16.2.6.3 Serious Adverse Events – Safety

Listing 16.2.6.4 AEs Leading to Discontinuation – Safety

Listing 16.2.6.5 AEs Leading to Death – Safety

All AEs will be displayed by subject including the PT of an AE, start and stop dates, duration and other characteristics of AEs.

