#### Table 15.2.6.1.T Summary of ECG Parameters – Safety

ECG parameters will be summarised using default summary statistics including change from baseline at each visit.

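### The primary objective is safety versus placebo, but the SAP plans no estimated active-minus-placebo difference or confidence interval for any safety variable

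*SAP*

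**What the plan says.** Protocol 2.1 states the primary objective: "To assess the safety profile of THN102 (modafinil/flecainide combination) at two doses (200 mg/18 mg and 200 mg/2 mg) versus placebo". SAP 2.1.1 repeats the comparator: "at two doses (200 mg/18 mg and 200 mg/2 mg) versus placebo". In Protocol 1.3.1 the sponsor gives as a reason for the design the wish to "take advantage of the cross-over design for exploring two doses of THN102 and comparing their impact on safety, ESS and other efficacy endpoints".

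SAP 5.5 fixes the population: "The safety set will be used for the analysis of the safety data". The planned safety analysis is descriptive in both documents:

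- **Protocol synopsis, safety analysis:** "Safety data will be summarised using summary statistics and frequency tabulations, as appropriate".
- **Adverse events:** Protocol 8.3.2 has "The number and percentage of subjects with adverse events will be tabulated by body system and preferred term with a breakdown by treatment". SAP 5.5.1 has "TEAEs will be summarised by displaying the numbers of adverse events, as well as counts and percentages of subjects having experienced adverse events".
- **ECG (SAP 5.5.4, Table 15.2.6.1.T):** "ECG parameters will be summarised using default summary statistics including change from baseline at each visit".
- **Vital signs (SAP 5.5.3):** summaries with change from baseline, low/normal/high categories and shift tables.
- **Laboratory, C-SSRS, MDS-UPDRS, QUIP-RS, physical examination:** summaries or frequencies, with shift tables for laboratory results.

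The default statistics in SAP 4.1 include the SD but no confidence interval. Baseline is a single value taken at or before VR (SAP 4.7) and is assigned to all treatments (SAP 4.8).

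For efficacy, mixed models with pairwise treatment contrasts are planned for ESS, PVT mean response time, MoCA and five actigraphy measures (SAP 5.6.1, 5.6.5 to 5.6.7).

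**The concern.** Each subject is meant to receive placebo and both doses, so the natural estimate for the primary objective is the within-subject difference from placebo. The SAP estimates that contrast for a secondary actigraphy measure such as daily jerk, but not for blood pressure, heart rate or QTcF.

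Change from baseline and shift tables are within-subject, but they refer to VR. They set each treatment period against the pre-treatment state, not active drug against placebo.

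What is at stake is how clearly the trial can say which effect sizes it rules out. Protocol 1.4.1 reports a small but significant rise in blood pressure and heart rate in phase I, and expects no cardiac effect from flecainide at the concentrations reached here. An interval for the difference from placebo would show how far the data support that expectation. Adjacent columns leave the reader to judge by eye.

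**Working it through.** **1. The plan's own figure.** The only power statement is for ESS: 54 subjects, effect size 0.40, paired t-test, two-sided 0.05, power 82% (Protocol 8.5, SAP 2.6). The noncentral t with 53 df and noncentrality 0.40 × √54 = 2.94 gives 82.3%, so the figure reproduces. Allowing 10% drop-out, 54 / 0.90 = 60, as stated. The documents give no precision figure for any safety variable.

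**2. Inputs for a continuous safety variable.** n = 54 completers (Protocol 4.1 and 8.5). No within-subject correlation is given, so ρ = 0.5 and 0.7 are assumptions. SD is the between-subject SD, taken as equal at VR and at each end-of-treatment visit, with the same ρ between any two visits.

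**3. Within-subject contrast, active minus placebo.** Half-width = t(0.975; 53) × SD × √(2(1−ρ)/54), with t = 2.006.

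- ρ = 0.5: 2.006 × √(1.0/54) = 0.273 SD
- ρ = 0.7: 2.006 × √(0.6/54) = 0.211 SD

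**4. Planned change-from-baseline columns read as independent.** The SD of change is SD × √(2(1−ρ)). Half-width = t(0.975; 106) × SD of change × √(2/54), with t = 1.983.

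- ρ = 0.5: 1.983 × 1.000 × 0.1925 = 0.382 SD
- ρ = 0.7: 1.983 × 0.775 × 0.1925 = 0.296 SD

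**5. Ratio.** 0.382 / 0.273 = 1.40 and 0.296 / 0.211 = 1.40. The ratio is √2 × 1.983 / 2.006 = 1.40, so under these assumptions it does not depend on ρ.

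**6. Raw columns instead of change columns.** Raw end-of-treatment columns read as independent give 1.983 × √(2/54) = 0.382 SD whatever ρ is. At ρ = 0.3 the paired half-width is 0.323 SD, so the raw columns are 0.382 / 0.323 = 1.18 times as wide. For correlations below 0.5 the raw columns are therefore the better of the two planned displays, and the loss is under 40%.

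**7. Adverse-event proportions.** Assume incidences of 10% and 20%, n = 54, and within-subject correlation φ from 0 to 0.4. Half-width = 1.96 × √{[0.1×0.9 + 0.2×0.8 − 2φ√(0.09×0.16)] / 54} = 1.96 × √[(0.25 − 0.24φ)/54].

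- φ = 0: 13.3 percentage points, the same as unpaired
- φ = 0.2: 12.0 points
- φ = 0.4: 10.5 points

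The narrowing at φ = 0.4 is 1 − √(0.154/0.250) = 22%, so the gain runs from 0 to about 22%.

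**The case against.** The other side has a good deal that stands.

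- **Placebo is shown.** Most safety tables are by treatment, with placebo as a column beside each dose. A reader might infer that safety is not compared with placebo at all. The documents do not support that. What is missing is an estimated difference with an interval.
- **The documents agree with each other.** The protocol prespecified descriptive safety reporting, the SAP follows it, and SAP 2.6 calls the trial exploratory. An objective to assess a safety profile does not oblige anyone to fit a model. There is no error of consistency here.
- **Paired precision is not lost beyond recovery.** Under the assumptions above, the SD of change from VR equals the SD of the active-minus-placebo difference, so t × SD of change / √n approximates the paired half-width. This is rough, because vital signs at VR average three sets against one at end of treatment, and drop-outs matter. Subject-level listings are also planned, but rebuilding paired differences from them would be an unplanned analysis.
- **The loss is not 80%.** That figure (0.382 / 0.211 = 1.81 at ρ = 0.7) sets raw columns against the paired contrast and ignores the planned change columns.
- **Period effects do not bias complete data.** The six sequences place each treatment twice in each period, with equal allocation. Additive period effects therefore cancel between raw treatment means in complete, balanced data. Only drop-out disturbs this.
- **The phase I signal came from higher doses.** The blood pressure and heart rate rises were seen at 400 mg modafinil, with or without 50 mg flecainide, above both doses studied here.

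None of this supplies the missing estimate. The objection that safety should not be formally tested in phase IIa does not apply to intervals reported without tests.

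**Conclusion.** The point holds as a cheap improvement to the SAP, not as an error. No safety section plans an active-minus-placebo difference or confidence interval, although that is the contrast named in the primary objective and the design was chosen partly with it in view. For continuous safety variables with planned change columns, treating those columns as independent gives a 95% interval about 40% wider than the within-subject contrast. That rests on 54 completers, equal variances and equal correlations. The documents give none of the correlations, and the loss is smaller if ρ is below 0.5 and the reader uses the raw columns.

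The case is strongest for vital signs and ECG intervals. For adverse events the gain is small under the rates and correlations assumed here. It would be going too far to conclude that the trial fails its primary objective or that the safety tables mislead. The tables are sound descriptions that stop one step short of the estimate the design makes available.

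**What to change.** Add to SAP 5.5.3 and 5.5.4, for the end-of-treatment values of supine and standing systolic and diastolic blood pressure, heart rate, PR, QRS and QTcF:

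- Fit the SAP 5.6.1 mixed model without the treatment-by-period interaction: fixed effects of treatment, period, sequence and baseline, with a random effect of subject within sequence.
- Assign data by treatment actually received, as SAP 4.8 already requires for safety.
- Report B minus A and C minus A with 95% confidence intervals, presented as estimates with no formal testing and no first-period rule.
- State whether heart rate is taken supine, standing or both.

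Optionally, report a paired risk difference with a 95% confidence interval for any TEAE.

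The cost is eight models, or nine if heart rate is modelled in both positions, each with two contrasts: 16 to 18 intervals. They use data already collected and code already written. No trial procedure or efficacy analysis changes. The downside is more exploratory output, with intervals not adjusted for multiplicity, which should be said in a footnote. If the outputs are added after unblinding, they should be labelled post hoc.

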### 5.5.1 Adverse Events

AEs will be coded according to MedDRA Version 21.0.

Adverse event data includes:

- adverse event name
- start date
- stop date or ongoing
- severity (mild, moderate, severe)
- relationship to the IMP (unrelated, unlikely, possible, probable, definite)
- action taken with IMP (no action, drug interrupted, drug withdrawn, unknown)
- other actions (none, medication required, tests required, hospitalisation required or prolonged, other)

- outcome (recovered/resolved, recovered/resolved with sequelae, recovering/resolving, not recovered/not resolved, fatal, unknown) and date of outcome
- serious (yes or no)

All AEs will be presented in listings.

Adverse event summaries will focus on **treatment-emergent adverse events (TEAEs)**, defined as AEs with an onset or worsening after the first IMP intake and not more than 7 days after the last IMP intake.

If the start date of an AE is incomplete or missing, it will be assumed to be treatment-emergent except if the stop date or the incomplete start date indicates that the event started prior to the first IMP intake or later than 7 days after the last IMP intake.

Treatment-emergent adverse events will be assigned to treatments based on the treatment period containing the AE onset date. If the onset date of an adverse event is during a washout period, it will be assigned to the preceding treatment period. If the AE onset date is incomplete such that it could belong to more than one treatment period, the AE will be assigned to all treatments corresponding to such treatment periods.

Based on collected data the following will be determined and will be used in addition to AEs overall for presentation in the applicable tables and listings:

- **Serious Adverse Events (SAEs):** defined as AEs considered by the investigator as serious.
- **Related TEAEs:** defined as AEs with relationships to the IMP assessed as being “possible”, “probable” or “definite” and include AEs with missing IMP relationship assessments.
- **Unrelated TEAEs:** defined as AEs with relationships to the IMP assessed as being “unlikely” or “unrelated”.
- **Severe TEAEs:** defined as AEs assessed as being “severe” in intensity and include the events with missing severity assessment.
- **TEAEs leading to discontinuation:** defined AEs whose action taken with IMP is “drug withdrawn” or other action taken is “withdrawal from trial”.
- **TEAEs leading to death:** selected as those events where outcome of event is indicated as “fatal”.

The **duration of the AE** will be calculated using the following formula:

$$AE \text{ Duration (days)} = AE \text{ stop date} - AE \text{ start date} + 1$$

If the start or stop dates of the AE are incomplete or AE is still ongoing at the end of the trial, the duration will not be calculated.

The following tables and listings will be provided:

Table 15.2.1.1.1.S Overall Summary of TEAEs – Safety

Table 15.2.1.1.2.T Overall Summary of TEAEs – Safety

An overview of TEAEs:

- TEAE
- Non-Serious TEAE
- Serious TEAE
- Related TEAE
- Related Serious TEAE
- Severe TEAE
- TEAE leading to discontinuation
- Serious TEAE leading to discontinuation
- Related TEAE leading to discontinuation
- TEAE leading to death

will be displayed for the subjects in the safety set.

Table 15.2.1.2.T Incidence of TEAEs – Safety

Table 15.2.1.3.T Incidence of Non-Serious TEAEs – Safety

Table 15.2.1.4.T Incidence of Serious TEAEs – Safety

Table 15.2.1.5.T Incidence of Related TEAEs – Safety

Table 15.2.1.6.T Incidence of Related Serious TEAEs – Safety

Table 15.2.1.7.T Incidence of TEAEs Leading to Discontinuation – Safety

Table 15.2.1.8.T Incidence of TEAEs Leading to Death – Safety

TEAEs will be summarised by displaying the numbers of adverse events, as well as counts and percentages of subjects having experienced adverse events. Percentages will be based on the number of subjects in the safety set. SOC and PTs within each SOC will be ordered by descending overall incidence.

Table 15.2.1.9.T Incidence of TEAEs by Severity – Safety

TEAEs will be summarised similarly as above within each adverse event severity level.

All adverse event data will be listed as follows:

Listing 16.2.6.1 Adverse Events: MedDRA Coding

Listing 16.2.6.2 Adverse Events: General – Enrolled

Listing 16.2.6.3 Serious Adverse Events – Safety

Listing 16.2.6.4 AEs Leading to Discontinuation – Safety

Listing 16.2.6.5 AEs Leading to Death – Safety

All AEs will be displayed by subject including the PT of an AE, start and stop dates, duration and other characteristics of AEs.

